## 9 STUDY EVALUATIONS

### 9.1 Study Procedures

#### 9.1.1 Overview

The Time and Events Schedules (see [Table 1](#) and [Table 2](#)) that follow the Synopsis summarizes the frequency and timing of safety, efficacy, pharmacodynamic biomarker, and other evaluations applicable to this study. Enrolled subjects will be assessed for eligibility according to the inclusion and exclusion criteria (see [Section 4.2](#) and [Section 4.3](#)).

Additional serum or urine pregnancy tests may be performed, as determined necessary by the investigator or required by local regulation, to establish the absence of pregnancy throughout the study. The total blood volume to be collected from each subject will depend on the amount of time they participate in this long-term study. The table in [Attachment 3](#) shows the maximum volume per each assessment. PRO assessments (ie, MCDSS) during a visit should be conducted before any tests, procedures, or other consultations for that visit.

The assessments per visit will vary as indicated per Time and Events schedules (see [Table 1](#) and [Table 2](#)). The required assessments at every dosing visit are:

- Weight
- Vital signs
- Review of adverse events
- Review of concomitant medications
- Administration of siltuximab

The follow-up Week 4 assessment (4 weeks after the last dose) will be considered as the end of treatment visit. During this visit, assessments will be repeated according to the Time & Events Schedules (see [Table 1](#) and [Table 2](#)) to conclude the study treatment and obtain follow-up details. The remainder of the follow-up period constitutes 2 visits, 8 and 12 weeks after the last administration during which serum blood samples will be collected to assess immunogenicity (antibodies to siltuximab) and biomarkers as applicable.

## 9.2 Safety Evaluations

Baseline chest X-ray is required within 3 months of first dose within this study and annually thereafter. If equivalent imaging (ie, CT, MRI) was performed for routine medical care at these timepoints, then it is allowed instead of a chest X-ray. Safety monitoring will consist of continuous AE reporting with a focus on infections, hyperlipidemia, neutropenia, thrombocytopenia, GI perforations, infusion-related reactions, liver enzyme abnormalities, and immunogenicity. ECG and clinical laboratory tests are to be performed according to the Time and Events Schedules. Other laboratory parameters will only be evaluated if clinically indicated. Any of these safety monitoring assessments may be performed more frequently if clinically indicated.

The study will include the following evaluations of safety and tolerability according to the timepoints provided in the Time and Events Schedules (see [Table 1](#) and [Table 2](#)):

- AEs and AEs  $\geq$  Grade 3
- SAEs
- Infusion reactions
- Clinically significant abnormal laboratory parameters
- Antibodies to siltuximab

The Medical Monitor will assess subject safety throughout the study on an ongoing basis. Safety will be evaluated using AEs, vital signs, weight, clinical laboratory parameters (hematology, chemistry, and lipid panel), and ECG as applicable. Any treatment-emergent clinically significant abnormalities persisting at the end of the study will be followed by the investigator until resolution or until a clinically stable endpoint is reached.

## Adverse Events

All toxicities will be graded according to the National Cancer Institute Common Terminology Criteria for Adverse Events (NCI-CTCAE, Version 4.0). Adverse events will be reported by the subject (or, when appropriate, by a caregiver, surrogate, or the subject's legally-acceptable representative) for the duration of the study. Adverse events will be assessed by the investigator as specified in [Section 12](#), Adverse Event Reporting.

For those subjects that do not have access to commercial siltuximab, continued siltuximab supply will be ensured. For all subjects still enrolled in the study after the 6-year data cutoff, only pregnancies and SAEs, including information on study agent administration and concomitant medications associated with an SAE, will be collected, and reported to the appropriate health authorities in safety update reports.

### **Clinical Laboratory Tests**

Blood samples for serum chemistry and hematology are collected according to the Time & Events Schedules (see [Table 1](#) and [Table 2](#)). The investigator must review the laboratory report, document this review, and record any clinically relevant changes occurring during the study in the adverse event section of the CRF. All laboratory reports have to be reviewed prior to the next study administration to evaluate subject's safety for continued treatment.

These tests will be performed by the local laboratory:

- **Hematology Panel**

The screening hematology laboratory sample must be collected > 2 weeks from last RBC transfusion, platelet transfusion, or neutrophil growth factor administration. Hematology results must be reviewed before the scheduled study agent administration to evaluate safety. After Amendment INT-4, only a limited hematology panel is required (see [Table 2](#)).

- hemoglobin
- WBC count with differential
- platelet count

- **Serum Chemistry Panel**

Serum chemistry results must be reviewed before the scheduled study agent administration to evaluate safety. After Amendment INT-4, only a limited serum chemistry panel is required (see [Table 2](#)).

- |                                  |                        |
|----------------------------------|------------------------|
| - sodium                         | - albumin              |
| - potassium                      | - total bilirubin      |
| - blood urea nitrogen/creatinine | - AST                  |
| - glucose                        | - ALT                  |
| - total protein                  | - alkaline phosphatase |

- **Coagulation Tests:** performed if clinically indicated.

- **Lipid Panel**

Fasting sample is required at screening, and is preferred for all subsequent samples. Lipid panel should be performed every 6 months. If the subject is naïve to siltuximab at study entry, the lipid panel should be done every 3 months for the first year of treatment, then every 6 months thereafter. If the lipid panel is abnormal, amylase and lipase may be assessed as clinically indicated.

- cholesterol
- HDL
- triglycerides
- LDL

- **Serum or urine pregnancy testing**

- For women of childbearing potential only at screening and Follow-up Week 4 visit, and as clinically indicated during the study.

- **Other tests**

- Quantitative immunoglobulins (IgG, IgA, IgM), to be performed only as clinically indicated

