
a. Siltuximab should be administered after all other study assessments and evaluations required at that visit. The visit window for siltuximab administration is minus 3 or plus 4 days from the scheduled visit date.
 
b. Blood samples for biomarker testing should be collected prior to study agent administration and at the end of treatment visit. A frequency of every 12 weeks means every 4th cycle for those on an every 3-week administration schedule and every 2nd cycle for those on an every 6-week administration schedule.
 
c. Scheduled blood samples for testing antibodies to siltuximab should be collected prior to study agent administration. Serum from venous blood samples (7.5 mL per sample) will be split into 3 aliquots (1 aliquot for analysis of antibodies to siltuximab, 1 aliquot for siltuximab serum concentration analysis to code antibodies to siltuximab data, and 1 aliquot as a backup). Serum concentration of siltuximab will also be determined at these timepoints. In addition, an unscheduled blood sample should be drawn, if possible, for determining antibodies to siltuximab any time an infusion-related reaction is observed during the study. This sample should be obtained as soon as possible after the reaction. A frequency of every 12 weeks means every 4th cycle for those on an every 3-week administration schedule and every 2nd cycle for those on an every 6-week administration schedule.
 
d. Serum samples for glycoform clearance analysis and in vivo protein degradation will be collected from 5 former study C0328T03 subjects (administered 11 mg/kg every 3 weeks) who consented to have these samples collected. These samples should be collected Cycle 1 (pre- and post-dose), and at Cycle 1 Day 3, Week 1 (Day 7 +/- 1 day), Week 2 (Day 14 +/- 2 days), and Week 3 (Day 21 +/- 2 days; before the Cycle 2 dose).
 
e. Vital signs will be measured predose and end of infusion on Day 1 of Cycle 1. Thereafter, vital signs will be measured only before each study agent administration on Day 1 of each cycle, and as clinically indicated.
 
f. ECGs will only be performed for those subjects who are siltuximab naïve at study entry, and as clinically indicated for all subjects.
 
g. Hematology and chemistry panel has to be performed prior to first dose to assess the subject's eligibility. If screening takes place within 7 days prior to first dose, the tests are not required to be repeated pre-dose Cycle 1. Laboratory monitoring will occur prior to each infusion in the first year of treatment for those subjects that are siltuximab-naïve at study entry.
 
h. Fasting sample is required at screening and preferred for subsequent samples. If lipid panel is abnormal, amylase and lipase may be assessed as clinically indicated.
 
i. Coagulation parameters should only be evaluated if clinically indicated.
 
j. If last chest X-ray was performed within 3 months prior to first dose, results can be used for the screening timepoint. If equivalent imaging (ie, CT, MRI) was performed for routine medical care at the timepoint, it is allowed instead of chest X-ray.
 
k. If considered to be clinically indicated, investigator assessment along with ESR, CRP, and fibrinogen evaluations, should be performed more frequently. Quantitative immunoglobulins should be performed if clinically indicated. Subjects who demonstrate disease progression on an once every 6 weeks dosing schedule (see Section 6.1) have to return to the every 3 weeks dosing schedule after reassessment of hematology and chemistry lab panels, physical exam, and, if not done within last 6 weeks, also a reassessment of investigator assessment of disease control and ESR, CRP, and fibrinogen.
 
l. Survival status after 5-year data cutoff will be collected twice a year for subjects still on treatment provided by Sponsor. For these subjects, SAEs, concomitant medications involved in treatment of SAEs, and information on pregnancies will continue to be collected. After treatment discontinuation, survival status, occurrence of malignancies, and subsequent therapies for MCD will be collected twice per year.
 
m. Only for subjects from the C0328T03 study; to be performed at the start of the screening visit, and predose at Cycles 1 and 2 (before other procedures).
							

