## 1.2 Potential Risks With Siltuximab

Because siltuximab is still in clinical development, its safety profile is not yet fully understood. Further investigation is necessary to better understand the safety of siltuximab. Therefore, unanticipated side effects that have not been previously observed may occur. Refer to the latest version of the siltuximab Investigator's Brochure for information regarding the safety of siltuximab.

A brief overview of the potential risks associated with the administration of siltuximab is outlined.

- Hypertriglyceridemia has been observed in some subjects who were administered siltuximab, and has been seen with other agents targeting the IL-6 receptor.
- Serious infections in single-agent studies have been reported in subjects administered agents that target IL-6 or its receptor. IL-6 directed therapy may have potential effects on humoral immunity. In addition, siltuximab may also potentially mask fever and other laboratory markers indicative of acute inflammation (eg, CRP). Therefore, subjects should be actively monitored for potential infection even in the absence of fever. Siltuximab should not be administered when there is evidence of serious active infection.
- Although unlikely, serious infusion related reactions (eg, anaphylaxis) may occur at any time during the administration of mAbs, including siltuximab.
- Administration of siltuximab may result in the development of antibodies against the protein. The risks of an anamnestic response to siltuximab are unknown.
- Gastrointestinal perforation has been reported in siltuximab clinical studies; however, these events are confounded by additional risk factors, including malignancy, abdominal surgery, and recent treatment with bevacizumab.
- Live, attenuated vaccines should not be given concurrently or within 4 weeks of initiating siltuximab, because clinical safety has not been established.
- IL-6 may serve as a growth factor for the bone marrow. Blocking IL-6 may therefore lead to decreases in neutrophils and platelets.

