6.4. Clinical Laboratory Tests

Safety evaluation of clinical laboratory tests will focus on the following selected laboratory analytes based on long-term safety extension study.

- Hematology panel: hemoglobin, platelet count, white blood cell (WBC) count with absolute neutrophils and lymphocytes
- Blood chemistry panel: sodium, potassium, creatinine, glucose, aspartate aminotransferase (AST), alanine aminotransferase (ALT), total bilirubin, alkaline phosphatase, uric acid, creatinine, phosphate and albumin.
- Lipid panel: cholesterol, triglycerides, HDL and LDL

Blood samples for serum hematology and biochemistry were taken at the screening visit, every cycle in 1st year for siltuximab-naïve subjects, every 3 cycles for 3-week regimen and every other administration visit at a minimum for those on 6-week regimen.

Descriptive statistics (mean, standard deviation, median, range) will be used to summarize observed laboratory values and change from baseline in observed value at each scheduled visit. Line plot of mean with SE for each laboratory analyte over time up to 6 years will be displayed for hematological parameters: hemoglobin, neutrophils, platelets, WBC, and biochemistry parameters: AST, ALT, creatinine, albumin, bilirubin, HDL, LDL, cholesterol, and triglycerides.

The worst toxicity grade in hematology and chemistry during siltuximab treatment will be summarized by toxicity grade. Shift tables from baseline to worst toxicity grade during siltuximab treatment will be provided for each laboratory analyte listed above. These tables will summarize the number of subjects with each baseline CTC grade and changes to the maximum CTC grade.

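### Lipid samples must be fasting at screening but need not be afterwards, and the SAP's triglyceride change and shift tables take no account of fasting status

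*Protocol*

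**What the plan says.** **Collection.** Protocol Section 9.2 (Clinical Laboratory Tests, Lipid Panel) states: "Fasting sample is required at screening, and is preferred for all subsequent samples". Footnote h to Table 1 gives the same rule: "Fasting sample is required at screening and preferred for subsequent samples". On frequency, Section 9.2 says "Lipid panel should be performed every 6 months", and for siltuximab-naïve subjects "the lipid panel should be done every 3 months for the first year of treatment, then every 6 months thereafter". Table 2 schedules a lipid panel at screening, none at pre-dose Cycle 1, and one at the end-of-treatment visit. The only scheduled pre-dose lipid value is therefore the one that must be fasting. The tests are run at local laboratories.

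**Analysis.** SAP 6.4 lists among its analytes "Lipid panel: cholesterol, triglycerides, HDL and LDL". Descriptive statistics are to "summarize observed laboratory values and change from baseline in observed value at each scheduled visit", and mean plots over time, triglycerides included, run to 6 years. It adds: "Shift tables from baseline to worst toxicity grade during siltuximab treatment will be provided for each laboratory analyte listed above". The SAP does not define a laboratory baseline. SAP 2.2 centres the laboratory analysis on the extension study.

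**Fasting status.** Neither document mentions recording it, analysing by it, or restricting any display to fasting samples.

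**Why lipids are watched.** Protocol Section 1.2 opens its risk list with this: "Hypertriglyceridemia has been observed in some subjects who were administered siltuximab". Hyperlipidemia is one of the focused safety events in Sections 3.2, 9.2 and 11.3.

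**The concern.** The sampling condition is fixed at baseline and left open at every later visit, and the analysis then subtracts one from the other. If food raises triglycerides (an assumption here, though the screening rule suggests the sponsor also thinks fasting matters), any non-fasting follow-up draw pushes the comparison upward. Shift tables are the most exposed, because they keep only the worst value per subject.

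Long-term safety is the primary objective. The study has one arm, so no comparison group would share the artefact and cancel it. SAP 6.3 gives separate subsections to infusion reactions, infections and secondary malignancies but none to hyperlipidemia. Apart from the general adverse event tables, the lipid displays in SAP 6.4 are the main quantitative evidence on this risk.

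**Working it through.** The plan states no triglyceride rate, non-fasting share or food effect, so there is no figure to reproduce. What follows is a sensitivity calculation.

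**Inputs from the documents:** the two lipid schedules (Section 9.2, Table 2) and a data cutoff about 6 years after the first enrolment (Section 3.1).

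**Assumptions, not in the documents:** q, the share of post-baseline draws that are non-fasting, is 10%, 25% or 50%; r, the ratio of non-fasting to fasting triglycerides, is 1.1, 1.2 or 1.3.

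**Step 1. Scheduled on-treatment draws over a full 6 years** (end-of-treatment panel not counted):
- previously treated: 6 × 2 = 12
- siltuximab-naïve: 4 + 5 × 2 = 14

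**Step 2. Inflation of the follow-up mean** = q × (r − 1):

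| q | r = 1.1 | r = 1.2 | r = 1.3 |
|---|---|---|---|
| 10% | 1% | 2% | 3% |
| 25% | 2.5% | 5% | 7.5% |
| 50% | 5% | 10% | 15% |

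**Step 3. Chance that a subject has at least one non-fasting draw** = 1 − (1 − q)^n if draws are independent. For example, 1 − 0.90^12 = 0.718.

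| q | n = 6 (3 years) | n = 12 | n = 14 |
|---|---|---|---|
| 10% | 47% | 72% | 77% |
| 25% | 82% | 97% | 98% |
| 50% | 98% | >99.9% | >99.9% |

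Independence pushes these figures up. If each subject either always or never fasted, the chance would simply be q: 10%, 25% or 50%.

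**Step 4. Effect on a shift table when the drug does nothing.** A simulation of 200,000 subjects assumed lognormal triglycerides with median 130 mg/dL, between-subject log-SD 0.45, within-subject log-SD 0.22 and an illustrative cut-off of 300 mg/dL. It counted subjects with a fasting baseline at or below the cut-off and a maximum of 12 draws above it.

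| q | r = 1.1 | r = 1.2 | r = 1.3 |
|---|---|---|---|
| 0% | 10.9% | 10.9% | 10.9% |
| 25% | 12.5% | 14.7% | 17.8% |
| 50% | 13.7% | 17.6% | 22.1% |

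The part due to food is the excess over 10.9%: 1.6 to 6.9 percentage points at q = 25%, and 2.8 to 11.2 points at q = 50%. The 10.9% itself comes from setting one baseline draw against the worst of 12, and it is there even when every sample is fasting.

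**Step 5. Direction against the true drug effect.** Suppose triglycerides rose by a fraction d in the parent study and then stayed level. The true ratio to the pre-drug value is 1 + d, while the extension tables show 1 + q(r − 1). They overstate if q(r − 1) exceeds d and understate if it is smaller. With q = 25% and r = 1.2 the break-even is d = 5%. The documents do not give d. For siltuximab-naïve subjects d = 0 at baseline, so the food artefact pushes upward only.

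**The case against.** - **Overstatement is not established.** A reader might infer that the tables overstate hypertriglyceridemia. The documents do not support that. Fasting stays the stated preference at every later visit, the non-fasting share is unknown, and most subjects enter on siltuximab (Section 3.1), so their baseline already contains any rise from the parent study. This stands.
- **Absence of a flag is not established.** A reader might also infer that samples carry no fasting mark. The CRF, the Laboratory Manual and the data presentation specification named in SAP 2.5 are separate documents, and the footnotes to Table 2 were not in the text available here. Only the silence of the protocol and SAP text reviewed can be asserted. This stands.
- **A rise could still be examined.** If the non-fasting share is steady, food produces one step after baseline rather than a trend, and follow-up visits can be compared with each other in the 6-year plots. This stands for the plots. It does not help change from baseline or the shift tables.
- **Twelve independent draws is a ceiling.** The cutoff runs from the first enrolment, subjects stop for progression, toxicity or withdrawal, and fasting habits probably cluster by subject or site. This stands, and Step 3 shows how far it lowers the figures.
- **Other evidence exists.** Investigators review laboratory reports and record relevant changes as adverse events (Section 9.2), hyperlipidemia is summarized as an event of clinical interest (Section 11.3), and lipid-modifying agents are still collected after Amendment INT-4 (Section 8). This evidence is affected only indirectly by fasting status.
- **Scope within SAP 6.4.** The worst-grade summary names hematology and chemistry, while lipids are listed as a separate panel. The shift tables are where lipids are clearly included.

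None of this removes the core point: the rule is asymmetric by design, and the planned displays ignore it.

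**Conclusion.** The point holds as a possible bias of unknown size. The fasting rule differs between baseline and follow-up, triglycerides enter the change, plot and shift displays, and no account of fasting status appears in the protocol or SAP. Follow-up values may be raised relative to baseline, most visibly in the shift tables.

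Under the assumed ranges (q 10% to 50%, r 1.1 to 1.3) the mean is inflated by 1% to 15%. For q of 25% to 50%, apparent shifts above the illustrative cut-off rise from 10.9% to between 12.5% and 22.1%. With nearly all later samples fasting, the effect is negligible. For subjects already on siltuximab, the net bias against the true drug effect could go either way.

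No hypothesis test, sample size or decision rule depends on these tables. This is a limit on interpreting descriptive safety output for a named risk, and it is worth correcting because the correction is cheap.

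**What to change.** 1. **Protocol 9.2 and CRF.** Record fasting status (yes, no, unknown) for each lipid panel from now on. If a flag already exists, refer to it.
2. **SAP 6.4, baseline.** State which sample is the lipid baseline.
3. **SAP 6.4, displays.** Keep the all-sample tables. Beside them, give triglyceride change from baseline and shift tables for fasting samples as a sensitivity display, with unknown status shown separately. Do the same for LDL where a laboratory calculates it; the documents do not say how LDL is obtained.

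**Cost.** One CRF field and one extra set of tables. If status was not captured before, earlier samples stay unknown: Amendment INT-4 is dated April 2014 and the original protocol November 2010. For that reason the fasting-only tables should be a sensitivity display, since making them the main analysis could discard much of the long-term data.

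**What it does not solve.** Comparing one baseline with the worst of many draws inflates shifts even when all samples are fasting. A footnote to the shift tables should say so.

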**Vital Signs (Temperature, Blood Pressure, and Heart Rate)**

Vital signs will be measured predose and end of infusion on Day 1 of Cycle 1. Thereafter, vital signs will be measured only before each study agent administration on Day 1 of each cycle, and as clinically indicated.

